## **8.1 Screening**

In general, it is permissible to re-screen a participant once if he/she fails the initial screening; however, each case must be discussed and agreed with the Sponsor on a case-by-case basis. A participant may not be enrolled in more than one treatment arm.

Further information on re-screening is outlined in the SOM.

### **8.1.1 Information to be collected on screening failures**

Certain limited data on screening failures will be collected. Further information on what data must be collected and further information on re-screening is outlined in the SOM.

### **8.1.2 Pre-screening**

Prior to the screening visit, optional pre-screening assessments may be conducted, including laboratory tests for serum albumin, ALT, AST, ALP, bilirubin, creatinine, ELF (or one of its component measures such as hyaluronic acid), HbA1c, INR, and platelets, in order to assess participant eligibility for inclusion. Prior to any assessments being conducted, the pre-screening informed consent form must be signed by the participant.

Only data related to SAEs causally related to study procedures (i.e., blood sampling) will be reported. All other data related to pre-screening will be recorded only in the source documentation.

## **8.2 Participant demographics/other baseline characteristics**

Country-specific regulations should be considered for the collection of demographic and baseline characteristics in alignment with CRF.

Participant demographic and baseline characteristic data are to be collected on all participants. Relevant medical history/current medical condition present before signing the informed consent will be recorded. Investigators will have the discretion to record abnormal test findings on the appropriate CRF whenever in their judgment, the test abnormality occurred prior to the informed consent signature.

## **8.3 Efficacy/Pharmacodynamics**

Efficacy of the single or combination drug regimens will be assessed based on the following three general classes of assessments:

- Liver function tests and liver and/or systemic inflammation markers (including ALT)
- Markers of liver fibrosis (including ELF Test)
- Magnetic Resonance Imaging (including MRI-PDFF)

In addition, the impact of treatment on cardiometabolic risk parameters including body weight, waist and hip circumference, waist-to-hip ratio, Homeostasis Model Assessment of Insulin Resistance (HOMA-IR), hemoglobin A1C (HbA1c), fasting glucose, fasting insulin, and fasting lipid profile will be assessed.

Pharmacodynamic (PD) samples will be collected at the timepoints defined in the Assessment schedule ([Table 8-1](#)). Follow instructions outlined in the central laboratory manual regarding sample collection, numbering, processing and shipment.

In order to better define the PD profile, the timing of the sample collection may be altered based on emergent data. The number of samples/blood draws and total blood volume collected will not exceed those stated in the protocol. PD samples will be obtained and evaluated in all participants at all dose levels.

### **8.3.1 Liver function tests and liver and/or systemic inflammation markers**

ALT, AST, GGT, ALP (total), total bilirubin, albumin, and high-sensitivity C-reactive Protein (hsCRP) will be assessed as indicated in the [Assessment schedule](#). The methods for assessment and recording are specified in the laboratory manual.

If the total bilirubin concentration is increased above 1.5 times the upper limit of normal, direct and indirect reactive bilirubin will be quantified.

ALP isoenzymes and 5' nucleotidase (5'NT) will also be measured but will not form part of the screening requirements or safety data set.

The methods for assessment and recording are specified in the laboratory manual. Some of the liver function tests may be completed as part of the blood chemistry panel.

### **8.3.2 Markers of Liver Fibrosis**

- Enhanced liver fibrosis Test (ELF TestTM) will assess: hyaluronic acid (HA), tissue inhibitor of metalloproteinases (TIMP-1), and amino-terminal pro-peptide of procollagen type III (PIIINP).
- Fibroscan® (optional) to assess liver stiffness (in kPa) will be performed where available. If Fibroscan is unavailable, alternative technologies to assess liver stiffness may be considered upon consultation with the sponsor.
- Fibrosis biomarker test (originally called Fibrotest®/ Fibrosure®) will assess:  $\alpha$ 2-macroglobulin, apolipoprotein A1, total bilirubin, haptoglobin, GGT, and ALT.
- Additional fibrosis markers may be assessed, including but not limited to FIB4 score, APRI score, and NAFLD score.

Additional information is provided in the central laboratory manual. These markers will be assessed as indicated in [Table 8-1](#) (Assessment schedule).

### **8.3.3 Magnetic Resonance Imaging (MRI)**

Participants will undergo magnetic resonance imaging twice during the course of the study (at Baseline and End of Treatment) to quantitate liver fat. Optional exploratory MRI-based assessments will be performed in a subset of participants to evaluate the effect of treatment on exploratory MRI related endpoints as outlined in [Table 2-1](#) (Objectives and related endpoints).

All participants who discontinue prematurely on or after Week 8 must have an end of treatment MRI assessment scheduled as close to the last dose of treatment as possible.

### 8.3.4 Anthropometric assessments

Height in centimeters (cm), waist and hip circumference (cm), and body weight (to the nearest 0.1 kilogram [kg] in indoor clothing, but without shoes), will be measured as indicated in [Table 8-1](#) (Assessment schedule). Additional details of these assessments will be provided in the SOM.

### 8.3.5 Cardiometabolic risk parameters

Blood samples will be collected for Homeostasis Model Assessment of Insulin Resistance (HOMA-IR), hemoglobin A1c (HbA1c), fasting glucose, fasting insulin, and fasting lipid profile including total cholesterol, HDL-cholesterol, LDL-cholesterol, triglycerides, and lipoprotein A as per [Table 8-1](#). Glucose and lipid measurements should be collected under fasted conditions. Detailed information will be provided in the central laboratory manual.

Note: Body weight, waist and hip circumference, and waist-to-hip ratio are also considered cardiometabolic risk parameters.

### 8.3.6 Appropriateness of biomarker assessments

As described in [Section 4.1](#), the three biomarkers supporting the secondary objectives of this study, liver fat content using MRI-PDFF, ALT and ELF Test are well established, platform technologies which are frequently used in both clinical practice and research in liver disease. Multiple studies in NAFLD and NASH conducted over the last five years have used some or all of these biomarkers as endpoints ([Sanyal et al 2017](#); [Harrison et al 2018a](#); [Harrison et al 2018b](#)).

## 8.4 Safety

Safety assessments are specified below with the Assessment schedule ([Table 8-1](#)) detailing when each assessment is to be performed.

The methods for each assessment and data recording details are located in the SOM.

For details on AE collection and reporting, refer to the AE [Section 10.1.1](#).

**Table 8-2 Physical Assessments**

Assessment	Specification
Physical examination	Complete physical examination will include the examination of general appearance, skin, neck (including thyroid), eyes, ears, nose, throat, lungs, heart, abdomen, back, lymph nodes, extremities, vascular and neurological. If indicated based on medical history and/or symptoms, rectal, external genitalia, breast, and/or pelvic exams may be performed. Focused physical examination will include the examination of general appearance, skin, throat, lungs, heart, abdomen, and extremities.
Vital signs	Includes body temperature, pulse, and blood pressure.

### 8.4.1 Safety-related laboratory evaluations

All abnormal lab results must be evaluated for criteria defining an adverse event and reported as such if the criteria are met. For those lab adverse events, repeated evaluations are mandatory

until normalization of the result(s) or until the result is no longer considered to be clinically significant.

**Table 8-3 Safety-related Laboratory Assessments**

Test Category	Test Name
Hematology	Hematocrit, Hemoglobin (HGB), Ery. Mean Corpuscular Hemoglobin (MCH), Ery. Mean Corpuscular HGB Concentration (MCHC), Ery. Mean Corpuscular Volume (MCV), Platelets, Erythrocytes, Leukocytes, Erythrocyte Morphology, Differential (Basophils, Eosinophils, Lymphocytes, Monocytes, Neutrophils, Bands, Other)
Chemistry	Albumin, Alkaline phosphatase, ALT, AST, Gamma-glutamyl-transferase (GGT), Lactate dehydrogenase (LDH), Bicarbonate, Calcium, Magnesium, Phosphate, Chloride, Sodium, Potassium, Creatinine, Creatine kinase, Direct Bilirubin, Indirect Bilirubin, Total Bilirubin, Total Cholesterol, LDL Cholesterol, HDL Cholesterol, Total Protein, Triglycerides, Blood Urea Nitrogen (BUN) or Urea, Uric Acid, Amylase, Lipase, HbA1c, Glucose
Urinalysis	Microscopic Panel (Erythrocytes, Leukocytes, Casts, Crystals, Bacteria, Epithelial cells) Macroscopic Panel (Dipstick) (Color, Bilirubin, Blood, Glucose, Ketones, Leukocytes esterase, Nitrite, pH, Protein, Specific Gravity, Urobilinogen)
Coagulation	Prothrombin time (PT), International normalized ratio (INR), Activated partial thromboplastin time (aPTT)
Pregnancy Test	Serum / Urine pregnancy test

#### **8.4.2      ECG**

Single 12 lead ECGs will be collected at the time points indicated in the Assessment schedule ([Table 8-1](#)).

PR interval, QRS duration, heart rate, RR interval, QT interval, QTc will be assessed.

The Fridericia QT correction formula (QTcF) must be used for clinical decisions.

As applicable, QTcF and QTcB may be calculated by study staff, unless auto-calculated by the ECG machine.

Clinically significant abnormalities must be reported as adverse events.

Additional details pertaining to ECG collection and reporting are included in the SOM.

#### **8.4.3      Pregnancy and assessments of fertility**

##### **Pregnancy testing**

See the Assessment schedule ([Table 8-1](#)), for timing of the protocol required pregnancy testing; additional pregnancy testing may be performed to meet local requirements\*. A positive urine pregnancy test requires immediate interruption of study treatment until serum  $\beta$ -hCG is performed and found to be negative.

\*Additional pregnancy testing might be performed if requested per local requirements.

Refer to [Section 10.1.4](#) for details on Pregnancy reporting.

## Assessments of Fertility

Refer to [Section 5.2](#) for criteria to determine a female participant's childbearing potential status.

Medical documentation of oophorectomy, hysterectomy, or tubal ligation must be retained as source documents. Subsequent hormone level assessment to confirm the woman is not of child bearing potential must also be available as source documentation in the following cases:

1. surgical bilateral oophorectomy without a hysterectomy
2. reported 12 months of natural (spontaneous) amenorrhea with an appropriate clinical profile.

In the absence of the above medical documentation, FSH testing is required of any female participant, regardless of reported reproductive/menopausal status at screening/baseline.

Vasectomized partners of female participants should provide supporting documentation, which is to be kept as source, as applicable per local Health Authority regulations.

### 8.4.4 Appropriateness of safety measurements

Other than possible treatment specific safety measures ([Section 17](#)), the safety assessments selected are standard for this indication/ participant population.

## 8.5 Additional assessments

No additional tests will be performed on patients entered into this study.

### 8.5.1 Clinical Outcome Assessments (COAs)

#### 8.5.1.1 Visual Analog Scale (VAS)

A 100 mm visual analogue scale (VAS) will be used to assess the severity of participants' itch (ranging from 0 = no itch at all to 100 = the worst imaginable itch). The score (distance from left) on the VAS will be recorded by the participant marking with a line.

The scale will be completed by participants as indicated in [Table 8-1](#) (Assessment schedule).

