**Table 8-1 Assessment Schedule**

Commercially Confidential Information

Epoch	Screening		Treatment												Post-Treatment Follow-Up 1 	Post-Treatment Follow-Up 2 				
	Visit Name	Screening	Baseline	Treatment												EOS1	EOS2			
Days	-60 to -28	-27 to -1	1 	8 	15 	22 	29 				43 	57 				71 	85 	113	141	
Weeks	-9 to -4	-4 to -1	1	2	3	4	5				7	9				11	13	17	21	
Time (post-dose)	-	-	-	-	-	-	0h 	1h	2h	3h	4h	-	0h 	1h	2h	3h	4h	-	-	
Demography	X																			
Hepatitis and HIV Screen 	S																			
COVID-19 Test 8a		S																		
Pregnancy and assessments of fertility 	X	X	X				X					X				X	X	X		
Physical examination 	S	S	S	S	S							S				S	S	S		
Vital signs and body measurements 	X	X	X	X	X							X	X			X	X	X		
ECG evaluation	X	X	X	X												X	X	X		
Hematology	X	X	X	X	X							X	X			X	X	X		
Blood chemistry	X	X	X	X	X							X	X			X	X	X		
Urinalysis	X	X	X	X	X							X	X			X	X	X		
Coagulation panel 	X	X	X	X	X							X	X			X	X	X		
Fasting glucose, insulin, and lipids 			X													X				
PK blood collection 			X	X	X	X	X	X	X	X	X	X	X	X	X	X 	X 			
Conditional biomarker RNA 		X	X									X				X	X	X		
Central lab biomarkers 	X 	X	X									X				X	X	X		

Commercially Confidential Information

Epoch	Screening		Treatment												Post-Treatment Follow-Up 1 	Post-Treatment Follow-Up 2 				
	Visit Name	Screening	Baseline	Treatment																
Days	-60 to -28	-27 to -1	1 	8 	15 	22 	29 				43 	57 				71 	85 	113	141	
Weeks	-9 to -4	-4 to -1	1	2	3	4	5				7	9				11	13	17	21	
Time (post-dose)	-	-	-	-	-	-	0h 	1h	2h	3h	4h	-	0h 	1h	2h	3h	4h	-	-	

Commercially Confidential Information

Dose administration 			X	X 	X 	X 	X					X 	X				X 	X 	
Fibroscan 24,25,NR			X														X	X 	
MRI/MRE 27,NR			X														X	X 	
VAS (Visual Analog Scale) 			X														X		
Telephone follow-up				X	X											X			

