Concomitant therapies 	X																		
Adverse events	As required																		
Serious adverse events	As required																		
Comments	As required																		
Study completion information																	X	X	

X Assessment to be recorded in the clinical database

S Assessment to be recorded in the source documentation only

NR Non-remote, i.e. this assessment may not be performed remotely (i.e., must be performed at the originally qualified facilities).

 For treatments with an extended half-life, EOS1 will be required as a standard, non-EOS post-treatment follow up visit, and EOS2 will serve as the EOS visit. For all other treatments, EOS1 will serve as the EOS visit.

 If a participant discontinues study treatment early, the participant should be scheduled for a subsequent visit at which time all assessments at the EOS1 visit should be performed. For treatments with an extended half-life, if a participant discontinues early after EOS1, then the participant should be scheduled for a subsequent visit at which time all assessments at the EOS2 visit should be performed.

 Assessments to be performed pre-dose.

 All participants must fast for at least 8 hours prior to administration of study treatment.

 Visit will be conducted via telephone only. Participants are not required to present to the study site for assessments.

 Informed consent must be provided by all participants before any screening procedures are performed. The DNA assessment is optional and requires a separate informed consent to be signed.

Commercially Confidential Information

 Standard laboratory assays to be used for screening.

8a COVID-19 test highly recommended to be completed within 1 week prior to first dosing, as defined in Exclusion Criterion #29.

 Serum pregnancy tests will be performed at Screening and EOS; urine tests may be used at other time points.

 A complete physical examination is required at Screening, Day 1, Day 85, and at the study completion visit. A focused physical examination can be performed at all other visits where a physical examination is required. Please see protocol [Section 8.4](#) for more details.

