 Body height only measured at Screening. Waist and hip circumference (for waist-to-hip ratio calculation) only measured at Baseline and Day 85. Blood pressure and pulse rate will be measured in a sitting position at all marked visits.

 Coagulation panel includes PT/INR and aPTT.

 Fasting glucose and insulin used for Homeostasis Model Assessment of Insulin Resistance (HOMA-IR) calculation. Fasting lipid panel includes total cholesterol, LDL, HDL, and triglycerides. Additional analyses of HDL and LDL sub-fractions, ApoC3, and lipoprotein(a) at these timepoints may be performed depending on the compound under investigation.

 Trough PK samples will be collected at all visits during the treatment period (Day 1 to Day 85). On Day 29 and Day 57, additional samples will be obtained as marked.

 Assessment is only to be performed at EOS if a participant discontinues study treatment and from the study early.

 Assessment may include (

CCI

Commercially Confidential Information

CRP,

CCI

ELF Test).

 ELF Test only.

Commercially Confidential Information

 For orally-administered study medications, participants will be provided with a supply to self-administer for 12 weeks (Day 2 to Day 84).

Study medication will be administered by study staff on marked visit days. Participants should bring all used and unused medications, and diaries, to each visit. For other types of study medications, such as injectable monoclonal antibodies, dose administration will be managed by study staff on marked visit days.

 Orally-administered study medications only.

 Optional assessment.

 If Fibroscan is unavailable, alternative technology to assess liver stiffness may be considered upon consultation with the sponsor.

 Assessment is only to be performed at this visit if a participant discontinues study treatment early on or after Week 8 for any reason and should be scheduled as closely to the last dose of treatment as possible.

 Assessment should be performed after eligibility is confirmed from all other screening/baseline assessments wherever possible. MRE is an optional

assessment. See Imaging Subject Scanning Guide for further instructions.

 VAS assessments for itching of the skin.

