## 6 Statistical methods for Efficacy/Pharmacodynamic (PD) parameters

All participants within the efficacy/PD analysis set will be included in the efficacy/PD data analysis.

Data will be excluded from the efficacy/PD analyses in the following cases:

- For participants with protocol deviations affecting the efficacy/PD analyses, the data will be excluded as described in [Table 4-1](#) above.
- For participants that discontinued treatment early, the following *programming rule* will be applied: *Any efficacy assessments that occurred on or after the treatment discontinuation study day, will be excluded from all efficacy/PD data analyses. An exception to this is the Day 85 visit or EOS visit imaging data (MRI and MRE assessments), that will be excluded only if they occurred prior to study day 56 (i.e., imaging assessments that occurred on or after study day 56, will not be excluded from the imaging analyses).*
- Participants with <80% treatment compliance

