## **8.1 Variables**

All safety data collected including adverse events, body height, body weight, BMI, vital signs (blood pressure, pulse rate and body temperature), ECG intervals (PR interval, QRS duration, heart rate, RR interval, QT interval, QTcF and QTcB), laboratory measurements (Hematology, Chemistry, Urinalysis, Coagulation and Pregnancy Test), as well as participant demographics, baseline characteristics, relevant medical history, current medical conditions, concomitant medications and significant non-drug therapies, and treatment information.

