## 11 SAP deviations from protocol

Commercially Confidential Information

2. In the study protocol V03 sections 12.5.1 and 12.6, the model used for analyzing secondary CCI parameters with more than one post-treatment measurement is named as '*repeated measures analysis of covariance (ANCOVA)*', whereas in the current SAP sections 6.2.3 and 6.3.3 it is named as '*mixed-effect model for repeated measures (MMRM)*', since this is a more appropriate wording for this model.
3. In the study protocol V03 section 8.5.1.1, it is stated that: '*A 100 mm visual analogue scale (VAS) will be used to assess the severity of participants itch (ranging from 0 = no itch at all to 10 = the worst imaginable itch).*' However, 100 is the correct VAS value corresponding to the worst imaginable itch, so in the current SAP section 6.3.1 this has been corrected accordingly to '*100 = the worst imaginable itch*'.

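### The itch VAS is not scheduled at the early-discontinuation visit, so its results describe only participants still on treatment at Day 85

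*Protocol*

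**What the plan says.** Protocol section 8.5.1.1 states that a 100 mm "visual analogue scale (VAS) will be used to assess the severity of participants' itch", from 0 (none) to 100 (worst), at the times given in Table 8-1. Footnote 28 to that table describes the row as "VAS assessments for itching of the skin" and gives no timing.

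The VAS row has two marks. The Fibroscan and MRI/MRE rows have marks in the same two positions plus a third at EOS1, which footnote 26 reserves for participants who stop treatment early, on or after Week 8. Protocol section 8.3.3 identifies the two shared positions: "Participants will undergo magnetic resonance imaging twice during the course of the study (at Baseline and End of Treatment) to quantitate liver fat". Under footnote 2, a participant who stops treatment early should be "scheduled for a subsequent visit at which time all assessments at the EOS1 visit should be performed". EOS1 has no VAS mark.

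In the SAP, the only visible reference to the VAS is section 11, item 3. It concerns the top anchor of the scale, "so in the current SAP section 6.3.1 this has been corrected accordingly to" a value of 100. Section 6.3 lies in the efficacy/PD chapter and its text is redacted. The opening of section 6 sets out exclusions:

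- "Any efficacy assessments that occurred on or after the treatment discontinuation study day, will be excluded from all efficacy/PD data analyses", with an exception only for imaging from study day 56.
- Participants with less than 80% treatment compliance.
- Data affected by the protocol deviations in Table 4-1, including TRT03.

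SAP section 4 adds that efficacy summaries at the EOS visit use study completers only. The safety variables in SAP section 8.1 open with "All safety data collected including adverse events, body height, body weight, BMI, vital signs" and do not name the VAS.

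**The concern.** Whether a VAS score exists depends on the thing being measured. Protocol section 9.1.1, item 8, requires treatment to stop for a CTCAE Grade 3 event suspected to be drug-related, liver and renal events apart. Severe itch attributed to study drug therefore leads to a visit at which itch is not scored. The other participants reach Day 85 and are scored.

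The two Cohort 1 arms differ by the addition of tropifexor to LYS006. If that addition changed the rate of stopping for itch, the Day 85 VAS would compare two differently selected groups, and the arm that lost more participants to itch would look relatively better on this scale.

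The VAS is the only directed, continuous, patient-reported itch measure visible in the plan. What is at stake is whether it can be read as describing everyone treated.

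**Working it through.** **1. Collection.** The columns of Table 8-1 are misaligned in the available text, so rows are compared with each other.

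| Row | Pre-treatment | End of treatment | EOS1 mark for early stoppers |
|---|---|---|---|
| MRI/MRE | yes | yes | yes (footnote 26) |
| Fibroscan (optional) | yes | yes | yes (footnote 26) |
| Itch VAS | yes | yes | no |

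Footnote 2 sends early stoppers to the EOS1 assessments. It follows that no VAS is scheduled for them after baseline. This step uses no redacted text.

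**2. What the SAP section 6 exclusions would do, if they govern the VAS.**

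*Stoppers.* The SAP formula is compliance = 100 × (expected − missed) / expected, with expected capsules counted up to the last treatment day. Full dose to Day 30 gives 100 × (30 − 0)/30 = 100%, so the compliance rule does not remove a stopper. The discontinuation rule would remove any VAS taken on or after the stop day.

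*Reducers.* Dose-change and interruption periods count towards missed capsules. Let T be the last treatment day, d the days at half dose (Table 6-3 says approximately one-half) and i the interrupted days. If the reduced dose is recorded as half the daily capsules, compliance = 100 × (T − 0.5d − i)/T.

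- Two days off, 14 days at half dose, then full dose, T = 85: 100 × (85 − 7 − 2)/85 = 89.4%. The compliance rule keeps this participant.
- d = 34, i = 0, T = 85: 100 × (85 − 17)/85 = 80.0%, kept. d = 35: 100 × (85 − 17.5)/85 = 79.4%, dropped. With T = 84 the threshold is 34 days.
- With a two-day interruption the threshold is 31 days (30 if T = 84).
- The exact reduced doses are redacted. At 40% or 60% of the starting dose, with no interruption, the threshold is 29 or 43 days.
- Table 6-3 path of 2 days off, 14 at half dose, w days back at the starting dose, then half dose to Day 85: for a first action on day s, d = 84 − s − w. Dropping below 80% needs d ≥ 31, so s ≤ 46 for w = 7 and s ≤ 39 for w = 14.

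**3. Size.** The plan gives no itch rate and no VAS distribution, so there is no figure to reproduce. For illustration, let k of 25 participants per arm stop for itch, with a mean score g mm above the rest. The mean among those still treated understates the all-treated mean by (k/25) × g. The upper value k = 5 comes from about 25 enrolled and 20 evaluable (Protocol section 5), a gap that covers every reason for being non-evaluable. The values of g are assumptions.

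| k | g = 40 mm | g = 60 mm |
|---|---|---|
| 1 | 1.6 | 2.4 |
| 3 | 4.8 | 7.2 |
| 5 | 8.0 | 12.0 |

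If one arm lost 1 and the other 5, with equal means among those remaining, the hidden between-arm difference would be (4/25) × g = 6.4 mm (g = 40) to 9.6 mm (g = 60).

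**The case against.** A reader might infer that the plan makes tolerability as a whole look better than it is. The documents do not support that. The primary endpoints are adverse events, laboratory measurements, vital signs, physical examination and ECG; the VAS is not named among them. Adverse events are sought at every visit (Protocol section 10.1.1). They are summarised in all treated participants by preferred term and maximum CTCAE grade, with separate summaries for drug-related events and events leading to discontinuation (SAP section 8.2). Itch in someone who stops or reduces stays in those tables. This objection stands. The limit is that non-directive questioning and coarse grades are not the same measurement as a directed continuous scale.

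A reader might also infer that scores from participants who reduce their dose are deleted. That is conditional: short reductions stay above 80% compliance. TRT03 is defined as treatment modification guidelines not being followed, so on its wording a reduction made according to the protocol is not a TRT03 deviation. Its criterion of more than two weeks at a decreased dose nevertheless overlaps the Table 6-3 path of remaining on the reduced dose to study completion.

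Three further points have weight:

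- SAP section 6.3 is redacted and may contain a VAS-specific rule. Applying the chapter's exclusions is an inference from one cross-reference, and the list in SAP section 8.1 is introduced as inclusive. The collection gap does not depend on this.
- Day 85 is inferred from row alignment. The missing third mark is a row-to-row difference that the broken columns do not explain.
- The protocol glossary lets a participant stop treatment and remain in follow-up, so some stoppers might attend Day 85. Any VAS taken then would be off treatment, and the discontinuation rule would exclude it if it applies.

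**Conclusion.** The point holds for the VAS itself. As scheduled, the scale describes participants still on treatment at Day 85. Those who stop early have no scheduled post-baseline score, and part of that missingness depends on itch severity. VAS results will tend to understate itch, and the between-arm VAS comparison could be distorted if itch-related stopping differs.

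It does not show that the primary tolerability assessment is biased, nor that reducers' scores are generally lost. Loss through the SAP exclusions is conditional on their applying to the redacted section 6.3. For reducers under the compliance rule, it also takes about 35 or more half-dose days.

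The size cannot be derived from the documents. The range of 1.6 to 12.0 mm rests on assumed scores and on attributing 1 to 5 losses per arm entirely to itch. In a non-confirmatory, open-label study this is a cheap improvement worth making.

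**What to change.** 1. **Protocol Table 8-1:** add a VAS mark at the early-discontinuation (EOS1) visit, as the MRI and Fibroscan rows already have, and apply it to every early stopper; the Week 8 limit in footnote 26 is not needed for this scale.
2. **SAP:** state that the VAS is summarised by arm in the safety analysis set, without the section 6 discontinuation and compliance exclusions, the TRT03 exclusion or the completers-only rule at EOS. Show the discontinuation-visit value alongside Day 85. The schedule change alone may not be enough, because those rules could remove the new score.
3. **Reconcile** the TRT03 criterion of more than two weeks at a decreased dose with the reduced-dose path in Protocol Table 6-3.

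Marks at other existing on-site visits, such as Days 29 and 57, are optional.

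The cost is SAP wording, one schedule mark and a single self-completed line at a visit already held. The burden on participants is slight. Itch may already be fading by the discontinuation visit, so the score could still understate on-treatment severity; recording the interval since the last dose would help readers judge this.
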